11.2 CLINICAL LABORATORY PARAMETERS

Descriptive statistics for clinical laboratory values (in SI units) and changes from the baseline values at each assessment time point will be presented by treatment group for the following laboratory parameters:

Hematology: red blood cells (RBC); white blood cells (WBC); WBC differential (% and absolute): neutrophils, lymphocytes, monocytes, eosinophils, basophils, hematocrit, hemoglobin, platelets

Blood Chemistry: albumin, alkaline phosphatase, alanine aminotransferase (ALT [SGPT]), aspartate aminotransferase (AST [SGOT]), total and direct bilirubin, blood urea nitrogen (BUN), calcium, chloride, creatinine, gamma glutamyltransferase (GGT), globulin, nonfasting glucose, potassium, total protein, and sodium

Urinalysis: color, appearance, specific gravity, pH, protein, glucose, ketones, occult blood, leukocyte esterase, nitrite, bilirubin, urobilinogen, crystals; microscopic examination if positive for protein, leukocyte, occult blood, nitrite, or crystals

Urine dipstick: The urine dipstick reagent test is used to identify a potential UTI and to provide immediate information to the investigator. If positive for nitrites and/or leukocyte esterase, indicating a possible infection, the participant should be treated with antibiotics per the clinical judgment of the investigator and in accordance with local site practice.

Urine cytology: Urine cytology is performed at the screening visit only. Abnormal urine cytology suspicious for a urothelial malignancy should be investigated by the investigator according to local site practice, and only if such malignancy is ruled out should the participant be enrolled.

Urine pregnancy: Urine pregnancy testing will be conducted for women of childbearing potential.

PSA: Prostate-specific Antigen (PSA) levels will be measured at screening in male participants.

Clinical laboratory test values will be considered potentially clinically significant (PCS) if they meet either the lower-limit or higher-limit PCS criteria listed in [Table 11.2-1](#). The number and percentage of participants who have PCS postbaseline clinical laboratory values will be tabulated by treatment group. The percentages will be calculated relative to the number of participants with available non-PCS baseline values and at least 1 postbaseline assessment for the double-blind treatment period. The numerator will be the total number of participants with available non-PCS baseline values and at least 1 PCS postbaseline value for the double-blind treatment period. A supportive tabular display of participants with PCS postbaseline values will be provided, including the PID number, baseline and all postbaseline (including non-PCS) values.

In addition, separate listings will be provided for each of the following clinical laboratory assessments:

- Participants with positive urine dipstick reagent test
- Participants with positive urine pregnancy test

Shift tables from baseline to end of study for clinical laboratory parameters will be presented by treatment group for the following categories: low, normal, and high, which are provided by lab vendor.

Table 11.2–1 Criteria for Potentially Clinically Significant Laboratory Results

Parameter	SI Unit	Lower Limit	Higher Limit
CHEMISTRY			
Albumin	g/L	< 0.9 × LLN	> 1.1 × ULN
Alanine aminotransferase	U/L	—	≥ 3 × ULN
Alkaline phosphatase (AP)	U/L	—	≥ 3 × ULN
Aspartate aminotransferase	U/L	—	≥ 3 × ULN
Bilirubin, total	μmol/L	—	> 1.5 × ULN
Calcium	mmol/L	< 0.9 × LLN	> 1.1 × ULN
Chloride	mmol/L	< 0.9 × LLN	> 1.1 × ULN
Creatinine	μmol/L	—	> 1.3 × ULN
Glucose, nonfasting	mmol/L	< 0.8 × LLN	> 1.4 × ULN
Potassium	mmol/L	< 0.9 × LLN	> 1.1 × ULN
Protein, total	g/L	< 0.9 × LLN	> 1.1 × ULN
Sodium	mmol/L	< 0.9 × LLN	> 1.1 × ULN
Blood Urea Nitrogen (BUN)	mmol/L	—	> 1.2 × ULN
HEMATOLOGY			
Basophils, absolute cell count	10 ⁹ /L	—	> 3 × ULN
Eosinophils	10 ⁹ /L	—	> 1.5 × ULN
Hematocrit	Ratio	< 0.9 × LLN	> 1.1 × ULN
Hemoglobin	g/L	< 0.9 × LLN	> 1.1 × ULN
Lymphocytes	10 ⁹ /L	< 0.8 × LLN	> 1.2 × ULN
Monocytes	10 ⁹ /L	< 0.5 × LLN	> 2 × ULN
Neutrophils, absolute cell count	10 ⁹ /L	< 0.8 × LLN	> 1.5 × ULN
Platelet count	10 ⁹ /L	≤ 0.5 × LLN	≥ 1.5 × ULN
Red blood cell count	10 ¹² /L	< 0.9 × LLN	> 1.1 × ULN
White blood cell count	10 ⁹ /L	≤ 0.7 × LLN	≥ 1.5 × ULN
URINALYSIS			
Glucose	mmol/L	—	Positive
pH	pH	< 0.9 × LLN	> 1.1 × ULN
Protein	g/L	—	Positive
Specific gravity	—	—	> 1.1 × ULN

LLN = lower limit of normal value provided by the laboratory; SI = *Le Système International d'Unités* (International System of Units); ULN = upper limit of normal value provided by the laboratory.

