Clinical laboratory test values will be considered potentially clinically significant (PCS) if they meet either the lower-limit or higher-limit PCS criteria listed in [Table 11.2-1](#). The number and percentage of participants who have PCS postbaseline clinical laboratory values will be tabulated by treatment group. The percentages will be calculated relative to the number of participants with available non-PCS baseline values and at least 1 postbaseline assessment. The numerator will be the total number of participants with available non-PCS baseline values and at least 1 PCS postbaseline value. A supportive listing of participants with PCS postbaseline values will be provided, including the PID number, baseline and all postbaseline (including non-PCS) values.

In addition, separate listings will be provided for each of the following clinical laboratory assessments:

- Participants with positive urine dipstick reagent test
- Participants with positive urine pregnancy test

Table 11.2-1. Criteria for Potentially Clinically Significant Laboratory Results

Parameter	SI Unit	Lower Limit	Higher Limit
CHEMISTRY			
Albumin	g/L	< 0.9 × LLN	> 1.1 × ULN
Alanine aminotransferase	U/L	—	≥ 3 × ULN
Alkaline phosphatase (AP)	U/L	—	≥ 3 × ULN
Aspartate aminotransferase	U/L	—	≥ 3 × ULN
Bilirubin, total	µmol/L	—	> 1.5 × ULN
Calcium	mmol/L	< 0.9 × LLN	> 1.1 × ULN
Chloride	mmol/L	< 0.9 × LLN	> 1.1 × ULN
Creatinine	µmol/L	—	> 1.3 × ULN
Glucose, nonfasting	mmol/L	< 0.8 × LLN	> 1.4 × ULN
Potassium	mmol/L	< 0.9 × LLN	> 1.1 × ULN
Protein, total	g/L	< 0.9 × LLN	> 1.1 × ULN
Sodium	mmol/L	< 0.9 × LLN	> 1.1 × ULN
Blood Urea Nitrogen (BUN)	mmol/L	—	> 1.2 × ULN
HEMATOLOGY			
Basophils, absolute cell count	10 ⁹ /L	—	> 3 × ULN
Eosinophils	10 ⁹ /L	—	> 1.5 × ULN
Hematocrit	Ratio	< 0.9 × LLN	> 1.1 × ULN
Hemoglobin	g/L	< 0.9 × LLN	> 1.1 × ULN
Lymphocytes	10 ⁹ /L	< 0.8 × LLN	> 1.2 × ULN
Monocytes	10 ⁹ /L	< 0.5 × LLN	> 2 × ULN
Neutrophils, absolute cell count	10 ⁹ /L	< 0.8 × LLN	> 1.5 × ULN
Platelet count	10 ⁹ /L	≤ 0.5 × LLN	≥ 1.5 × ULN
Red blood cell count	10 ¹² /L	< 0.9 × LLN	> 1.1 × ULN
White blood cell count	10 ⁹ /L	≤ 0.7 × LLN	≥ 1.5 × ULN
URINALYSIS			
Glucose	mmol/L	—	Positive
pH	pH	< 0.9 × LLN	> 1.1 × ULN
Protein	g/L	—	Positive
Specific gravity	—	—	> 1.1 × ULN

LLN = lower limit of normal value provided by the laboratory; SI = *Le Système International d'Unités* (International System of Units); ULN = upper limit of normal value provided by the laboratory.

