15.9 CHARACTER VALUES OF CLINICAL LABORATORY PARAMETERS

If the reported value of a clinical laboratory parameter cannot be used in a statistical summary table because, for example, a character string is reported for a parameter of the numeric type, a coded value must be appropriately determined for use in the statistical analyses. The actual values, however, as reported in the database will be presented in the data listings.

shows examples of how some possible laboratory results should be coded for the analysis
[Table 15.9-1](#).

[figure not shown]
Table 15.9-1 Examples of Coding Special Character Values for Clinical Laboratory Parameters

Laboratory Test, SI Unit	Possible Laboratory Results	Coded Value for Analysis
CHEMISTRY		
ALT, U/L	< 5	5
AST, U/L	< 5	5
Bilirubin, total, μ mol/L	< 2	2
URINALYSIS		
Glucose, mmol/L	= OR $> 55, \geq 55, > 0$	Positive
	≤ 0 , negative	Negative
pH	$> 8.0, \geq 8.0$	8.0
	≥ 8.5	8.5
Protein	= OR $> 3.0, \geq 3.0, > 0$	Positive
	≤ 0	Negative

ALT = alanine aminotransferase; AST = aspartate aminotransferase; SI = *Le Système International d'Unités* (International System of Units).

[figure not shown]
16.0**CHANGES TO ANALYSES SPECIFIED IN PROTOCOL**

It is stated in [protocol](#) that all ANCOVA models will include both stratification factors (sex and baseline UUIEs per day) as independent variables. However, some of the ANCOVA models include only sex (male, female) due to the high correlation (observed in previous Allergan studies) between baseline UUIEs (≤ 9 or > 9 episodes/day) and some of the dependent variables derived from the bladder diary data.

ALLERGAN

1839-201-021 Statistical Analysis Plan for Stage 2

Date (DD/MMM/YYYY)/Time (PT)	Signed by:	Justification
10-Jan-2020 15:12 GMT-080		Biostatistics Approval
11-Jan-2020 07:23 GMT-080		Biostatistics Approval
13-Jan-2020 12:58 GMT-080		Biostatistics Approval
15-Jan-2020 08:23 GMT-080		Clinical Development Approval

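### The specific gravity PCS limit in Table 11.2-1 of both SAPs cannot be reached, the upper pH limit may not be, and occult blood, leukocyte esterase and nitrite have no PCS row

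*SAP*

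**What the plan says.** Section 11.2 of both SAPs sets the rule: "Clinical laboratory test values will be considered potentially clinically significant (PCS) if they meet either the lower-limit or higher-limit PCS criteria listed in" Table 11.2-1. Table 11.2-1 of each SAP (Section 11.2) has the same four urinalysis rows:

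- glucose: "Glucose mmol/L — Positive"
- pH: "< 0.9 × LLN > 1.1 × ULN"
- protein: "Protein g/L — Positive"
- specific gravity: "Specific gravity — — > 1.1 × ULN"

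The limits of normal are not printed. The footnote reads "ULN = upper limit of normal value provided by the laboratory". On reporting, both SAPs state: "The number and percentage of participants who have PCS postbaseline clinical laboratory values will be tabulated by treatment group". The denominator is participants with a non-PCS baseline and at least one postbaseline assessment. The numerator is those among them with at least one PCS value after baseline.

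The urinalysis list in Section 11.2 of both SAPs also includes occult blood, leukocyte esterase and nitrite. None of the three has a row in Table 11.2-1.

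Table 15.9-1, titled "Examples of Coding Special Character Values for Clinical Laboratory Parameters", codes high pH strings as 8.0 or 8.5.

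**The concern.** A multiplier of 1.1 suits analytes measured from zero. Specific gravity is a ratio to water that starts at 1.000, so ten per cent above its upper limit is not a modest excess over normal but a value far outside the scale of urine. A row built that way prints zero in every arm whatever happens to the participants, and a reader of the report could take those zeros as reassurance.

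The analytes more likely to move after a bladder instillation are blood, leukocyte esterase and nitrite. Protocol Section 9.4.3 treats positive results for these as suggestive of urinary tract infection (UTI), and Protocol Section 10.1 names UTI as one of two adverse events of particular interest. Urinalysis is a listed safety measure (Protocol Section 4). What is at stake is whether the PCS table adds anything on urinary safety by dose.

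**Working it through.** The plan gives no numerical cut-off to reproduce, so the check applies the table's multipliers to assumed laboratory limits.

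**Inputs from the documents:** multipliers 1.1 (upper) and 0.9 (lower), from Table 11.2-1; coded pH values 8.0 and 8.5, from Table 15.9-1.

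**Assumptions:** specific gravity ULN 1.020 to 1.040; pH ULN 7.0 to 8.5; pH lower limit of normal (LLN) 4.5 to 5.5; a generous urine maximum for specific gravity of 1.060.

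**Specific gravity.** Cut-off = 1.1 × ULN.

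| ULN | Cut-off |
|---|---|
| 1.000 (water) | 1.100 |
| 1.020 | 1.122 |
| 1.025 | 1.1275 |
| 1.030 | 1.133 |
| 1.035 | 1.1385 |
| 1.040 | 1.144 |

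In reverse: to flag a result of 1.060, the ULN would have to be below 1.060 / 1.1 = 0.964, which is less than water. There is no lower criterion, so the row cannot fire.

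**pH, upper limit.** Cut-off = 1.1 × ULN.

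| ULN | Cut-off | Coded 8.0 flags? | Coded 8.5 flags? |
|---|---|---|---|
| 7.0 | 7.70 | yes | yes |
| 7.5 | 8.25 | no | yes |
| 8.0 | 8.80 | no | no |
| 8.5 | 9.35 | no | no |

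Break-even ULNs: 8.0 / 1.1 = 7.27 and 8.5 / 1.1 = 7.73. A reported 9.0 would flag if the ULN were below 9.0 / 1.1 = 8.18.

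**pH, lower limit.** Cut-off = 0.9 × LLN. An LLN of 4.5, 5.0 or 5.5 gives 4.05, 4.50 or 4.95. A pH of 4.5 would flag only with an LLN above 5.0.

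**Where the three analytes without a PCS row do appear:**

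- By-visit summaries by treatment group (Section 11.2 of both SAPs), with number and percentage for categorical variables (Section 11.0 of both). These give positivity at each visit, not a participant-level rate over the study.
- Low/normal/high shift tables, in the Stage 2 SAP only, from baseline to end of study. Stage 2 SAP Section 15.1 defines that endpoint as Week 24 or the exit visit, so a change that appears and resolves in between is not seen. The three categories may also not suit positive/negative results.
- Positive dipsticks: listed, not tabulated. Protocol Section 9.4.3 names nitrites and leukocyte esterase as the dipstick triggers, not blood.
- Adverse events (Protocol Section 9.2.6): UTI needs symptoms, culture and leukocyturia together. Asymptomatic bacteriuria or leukocyturia is reported if clinically significant. Asymptomatic occult blood has no specific rule.

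None of these yields the proportion newly positive at any time, by arm.

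**The case against.** The best case against acting is that a bladder signal would surface elsewhere. UTI has its own adverse event definition. Treatment-emergent events are tabulated by arm, severity and causality, including causality to the instillation procedure (Section 11.1 of both SAPs). The three analytes are summarised by arm at each visit. A negative dipstick for nitrite and leukocyte esterase is required on the day of treatment (Protocol Sections 7.1.2 and 9.4.3), so later dipstick positives are in effect new. For specific gravity, the Stage 2 shift tables already use the laboratory range without a multiplier, and no one has shown that high specific gravity would signal harm from this product. A reference-range rule would also be looser than most other numeric PCS limits in the table.

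Much of this stands, and it limits the point to one display. A reader might infer that the urinalysis PCS table can show nothing, or that blood and infection markers are not reported by dose at all. The documents do not support either reading: the glucose and protein rows fire on any positive result, and by-arm summaries and adverse event tables are planned. Nor can one say that the pH row never fires. That depends on the laboratory range, and Table 15.9-1 offers examples of coding, not a ceiling on results.

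The objection does not rescue a threshold that cannot be met, and it does not supply an any-time rate. The dipstick listing comes closest, but it would have to be counted by hand and its named triggers omit blood.

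**Conclusion.** The point holds, as a minor defect of the PCS display.

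- **Specific gravity:** the row is inert for any ULN of 1.000 or more, given only that urine does not reach 1.100. Its 0% in every arm is not safety evidence.
- **pH:** the upper criterion is inert for the coded values if the laboratory's ULN is 7.73 or higher, and active for a coded 8.5 below that. The documents do not settle which applies.
- **Occult blood, leukocyte esterase, nitrite:** collected and summarised by arm and visit, but without an any-time, newly positive rate by dose in either SAP. Both SAPs place table specifications in a separate document not available here, which might add one.

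Nothing here affects the primary efficacy analysis, the sample size or data collection.

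**What to change.** In Table 11.2-1 of both SAPs:

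1. Delete the specific gravity row, or replace the multiplier with the laboratory reference range.
2. Obtain the laboratory's pH limits and compute 0.9 × LLN and 1.1 × ULN. If reportable results cannot cross them, treat pH the same way.
3. Add rows with the criterion Positive for occult blood, leukocyte esterase and nitrite, as already used for glucose and protein. The existing non-PCS-baseline numerator and denominator then give the newly positive proportion by arm with no further rule.

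The cost is a table edit in each SAP and a few more output rows from data already collected. More participants will be flagged, and a reference-range rule for specific gravity or pH would be less strict than most other numeric rows; deleting those rows avoids that.

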11.3 VITAL SIGNS

Descriptive statistics for vital signs (systolic and diastolic blood pressures, pulse rate, temperature and weight) and changes from baseline values at each visit will be presented by treatment group.

Vital sign values will be considered PCS if they meet both the observed-value criteria and the change-from-baseline criteria listed in Table 11.3-1. The number and percentage of participants with PCS postbaseline values will be tabulated by treatment group. The percentages will be calculated relative to the number of participants with available baseline values and at least 1 postbaseline assessment. The numerator will be the total number of patients with available baseline values and at least 1 PCS postbaseline value. A supportive listing of participants with PCS postbaseline values will be provided, including the PID number, baseline and all postbaseline (including non-PCS) values.

Table 11.3-1. Criteria for Potentially Clinically Significant Vital Signs

Parameter	Flag	Criteria^a	
		Observed Value	Change From Baseline
Sitting systolic blood pressure, mm Hg	High	≥ 150	Increase of ≥ 20
	Low	≤ 90	Decrease of ≥ 20
Sitting diastolic blood pressure, mm Hg	High	≥ 100	Increase of ≥ 15
	Low	≤ 50	Decrease of ≥ 15
Sitting pulse rate, bpm	High	≥ 100	Increase of ≥ 15
	Low	≤ 50	Decrease of ≥ 15
Weight, kg	High	—	Increase of ≥ 7%
	Low	—	Decrease of ≥ 7%
Temperature, °C	High	> 38	—
	Low	< 35	—

a A postbaseline value is considered potentially clinically significant if it meets both the observed-value and the change-from-baseline criteria.

bpm = beats per minute.

11.4 OTHER SAFETY PARAMETERS

11.4.1 Physical Examination

Physical examination will be performed at screening and at study exit visit. All findings at the screening visit will be recorded on the Medical and Surgical History/Physical Findings eCRF page. Any new or worsening condition observed at the study exit visit will be recorded on the Adverse Event eCRF page. Hence summaries for physical examinations will be captured in summaries presented for medical and surgical history and adverse events.

11.4.2 Post-Void Residual Urine Volume

Descriptive statistics for PVR urine volume (mL) and changes from baseline values at each visit and at the end of study will be presented by treatment group. In addition, the number and percentage of participants with PVR urine volume within each of the following categories will be presented by treatment group for each postbaseline visit as well as for the entire study:

- < 100 mL
- \geq 100 mL and < 200 mL
- \geq 200 mL and < 350 mL
- \geq 350 mL

11.4.3 Bladder and Kidney Ultrasound

A listing of all participants with at least one pre-existing or new bladder or kidney condition will be provided for the Safety Population by treatment group.

11.4.4 Concurrent Procedures

Concurrent procedures will be presented in a listing together with the indication for which the procedure was performed. The indication will be coded using MedDRA system organ class and preferred term.

11.4.5 Catheterization Use

The number and proportion of participants catheterizing will be summarized, broken out by reason (for urinary retention or for other reasons) and whether it was CIC or not. This will be determined from the Catheterization eCRF.

12.0 INTERIM ANALYSIS

No interim analysis is planned for this study. However, in Stage 2, a primary analysis will be conducted when all randomized participants have completed at least 12 weeks of follow-up post-randomization (or prematurely exited the study prior to Week 12). The final analysis will be performed after study completion. There will be 2 database locks for Stage 2: one for primary and one for final analysis.

The purpose of the primary analysis is to identify early trends in the data for administrative planning of phase 3 studies. Specifications of tables, figures, and data listings to be generated during the primary analysis are provided in a separate document.

On completion of the primary analysis, the study will be unblinded to Allergan personnel. However, investigators and study sites personnel will remain blinded until completion of the final analysis.

13.0 DETERMINATION OF SAMPLE SIZE

For Stage 2, 50 participants are required for each of the 4 BOTOX treatment groups and 50 participants are required for the placebo group in order to obtain approximately 72% power to detect a between group difference of 1.8 episodes in change from baseline to week 12 in the number of episodes of urinary incontinence per day between the BOTOX and placebo treatment groups. Sample size calculations are based on a two-sample t-test assuming a common standard deviation (SD) of 3.5 episodes and a 2-sided type I error rate of 0.05. In order to account for participant attrition (estimated to be 5%), the sample size was increased to 53 participants for each treatment group, amounting to a total of 265 randomized participants required for Stage 2. Additionally, using these samples sizes, the probability of observing at least one occurrence of urinary retention or UTI in the BOTOX-treated population in Stage 2 is nearly 1.

14.0 STATISTICAL SOFTWARE

Statistical analyses will be performed using version 9.2 (or newer) of SAS on a Linux operating system.

15.0 DATA HANDLING CONVENTIONS

15.1 STATISTICAL ANALYSIS VISIT WINDOWS

Table 15.1-1 presents the visits assigned for efficacy and safety analyses and the corresponding range of treatment days (window) during which an actual visit may occur.

Table 15.1-1. Statistical Analysis Visit Windows

Derived Visit	Scheduled Visit Day^a	Window
Baseline	Day 1	Days \leq 1
Week 2	Day 15	Days [2, 29]
Week 6	Day 43	Days [30, 64]
Week 12	Day 85	Days [65, 99]
Week 16	Day 113	Days [100, 127]
Week 20	Day 141	Days [128, 155]
Week 24	Day 169	Days \geq 156
End of study ^b	Week 24 or Study Exit Visit	

a Relative to the date of the study treatment. Day 1 = the date of the study treatment.

b Presented in analysis tables for safety parameters, including but not limited to electrocardiograms, clinical laboratory values, and vital signs. If a participant completes the study, the Week 24 visit is the end of study visit. If a participant discontinues the study prematurely, their last study visit (study exit visit) is the end of study visit.

If the assessment date (if the assessment date is unavailable, use visit date instead) is on or after the date of the of study treatment, the study day is calculated by assessment date – date of the of study treatment + 1. If the assessment date is before the date of the study treatment, the study day is calculated by assessment date – date of the study treatment. Therefore, a negative day indicates a day before the start of the study treatment. There is no Day 0; day of randomization and study treatment is Day 1.

[figure not shown]
If a participant has 2 or more visits within the same window, the last visit with a nonmissing value will be used for analysis. All postbaseline assessments will be considered for PCS categorization. All assessments will be included in respective listings.

